7.3 Pharmacodynamic Studies in tumor tissues

7.3.1 Serial Tumor Biopsies and analysis.

Optional serial tumor biopsies are included in the budget for this study. We anticipate that 5 patients will complete at least two serial biopsies (10 total biopsies). Biopsy of easily accesible lesions that do not require radiological guidance will be conducted either by the medical oncologists, surgical oncologist, dermatologists or dermatological surgeons. The procedures involved include: excisional biopsies, excisions of large tumors in the operating room, and core needle biopsies. For core needle biopsies we request 4 cores if possible. The radiologist m ay choose the size of the needle. Lesions that are not easily accesible can be biopsied with the assistance of imaging guidance. This will involve core needle biopsies conducted by a radiologist. Processing of cores will be as follows:

- Core 1) formalin- provided by the institution's pathology department. Sample is processed through surgical pathology. Once all samples are obtained, or at an intermediate timepoint in the study, a request for 20 unstained slides or the tissue block from this specimen will be made.
- Core 2) snap frozen.- handled by institutions path department. Samples should be stored at -80°C or in liquid nitrogen until batch shipment on dry ice.
- Core 3) EM fixative- provided by [name] lab (please email [contact] to request EM fixative).
- A sesame seed size sample of tissue can be fixed in EM fix and stored at 4°C (regular refrigerator) until batch shipment.

Core 4) additional research sample

Timepoints for serial tumor biopsies will be

- 1) baseline
- 2) C1D21 ± 7 days

These timepoints may be changed/modified at the discretion of the prinicipal investigator/study chair since the precise timing of successfully measuring the biological effect of drug intervention is not known.

7.3.2 Measuring autophagy induction and autophagy inhibition in tumor tissue.

Currently the gold standard techniques for detection of autophagy in tissues are 1) electron microscopy (EM) and 2) immunoblotting against the autophagy protein LC3. The accumulation of characteristic double-membrane vesicles in cells can be quantified by EM. When autophagy is induced by cellular stresses, small AV can be detected with well-digested contents. When autophagy is inhibited with CQ derivatives, larger and more numerous AV with undigested contents accumulate. When AV vesicles accumulate, LC3 is cleaved to form LC3-I and LC3-II³⁹. LC3-II is inserted into the membranes of AV making it a specific marker for AV formation. The ratio between LC3I and LC3II as measured by immunoblotting reflects the number of AV accumulated. The inhibition of autophagy with CQ derivatives leads to a rapid accumulation of AVs in tumor tissue. This can be measured by scoring the number of AV/cell by EM in tumor tissue²⁴.

7.3.3 Therapy-induced gene expression changes in the tissue microenvironment.

In order to best understand the mechanism of action, resistance and interaction with the tumor microenvironment for dabrafenib, trametinib and HCQ, mRNA expression analysis or proteomic analysis is best suited to provide a snapshot of each of these effects. We will use the Quantigene® platform (http://www.panomics.com/index.php?id=product 6) because it is compatible with both fresh and FFPE tumor tissue. The array will be customized and enriched for genes associated with the inflammatory response, kinase signaling pathways, and stress response pathways such as the endoplasmic reticulum (ER) stress response and autophagy. We anticipate there will be a total of 10 tissue samples from 5 patients from the phase II trial including pre -treatment, on treatment that are large enough to warrant this sort of analysis.

7.4 Blood based correlative studies

7.4.1 Plasma biomarkers for autophagy dynamics

Rationale: Recent published data suggests that autophagy is not only involved in degradation of dysfunctional proteins but also plays a role in the maturation and secretion of functional proteins as well. By profiling the tumor secretome in cell culture and mouse xenograft model, we have

identified a number of candidate proteins. These have been validated in human samples, and in vitro data demonstrate elevations in IL-8, Interleukin-1 Beta, LIF, DKK3, and FAM3C in high autophagy states compared to low autophagy states. (Kraya Autophagy 2015). We therefore propose to analyze plasma concentrations of these proteins in the presence and absence of HCQ and compare them to the gold standard of electron microscopy. We can then determine whether these proteins would be useful as an non-invasive biomarker of autophagy dynamics.

7.4.2 Methods for Collecting Plasma

Supplies (to be purchased and maintained by each institution's clinical research lab)

- Purple top EDTA Blood Collection Tubes (for example, BD vacutainers catalog # 366450)
- Centrifuge with swinging bucket rotor
- 15 ml polypropylene conical tubes (for example, Corning 430052, Fisher cat #05-538-53D)
- Sterile cryovials with writing surface (for example, Simport T311-2 or Fisher #05-669-57)
- 2ml, 5ml and 10 ml pipettes (for example, Fisher cat #13-678-11C, 13-678-11D, 13-678-11E)
- Disposable transfer pipettes (for example, Fisher cat #13-711-20)
- Automatic pipet aid
- Small ice bucket

Plasma Collection Procedure

- 1) At each time point, encourage filling of entire volume of 1 purple top EDTA tube:
- After collection, gently mix the blood by inverting the tube 8 to 10 times. Store vacutainer tubes upright at 4°C until centrifugation. Blood samples should be centrifuged within three hours of blood collection.
- Centrifuge blood samples in a horizontal rotor (swing-out head) for 10 minutes at 1200 g (2500 rpm) at room temperature.
- 4) After centrifugation, plasma layer will be at the top of the tube. Mononuclear cells and platelets will be in a whitish layer, called the "buffy coat", just under the plasma and above the red blood cells
- 5) Collect plasma layer into a second tube. Spin secondary tube at 1200 xg (2500 rpm) for 5 mins. To remove remaining red blood cells.
- 6) Aliquot plasma (~4 ml) into cryotubes (500 µl per tube).
- 7) Transfer to -80 °C for archival storage. NOTE: Time from blood draw until freezing should be less than 3 hrs. (if greater than 3 hrs., note time and flag samples, but do not discard). Do NOT store blood at 4 °C.

Plasma Data points

- 1. Date and time of blood collection
- 2. Number and volume of aliquots prepared
- 3. Date and time into -80°C

- 4. Date and time of shipping
- 5. Any freeze-thaw that occurs with a sample for any reason
- 6. Any variations or deviations from the SOP, problems, or issues

7.4.3 FFPE archival tumor tissue for genetic analysis.

For all patients enrolled, we plan to obtain 20 unstained slides from archival FFPE blocks of ideally the latest metastatic lesion that was biopsied. 10 slides will be submitted for Myseq® multiplex DNA sequencing using the Illumina Truseq Cancer Panel (http://www.illumina.com/products/truseq amplicon cancer panel.ilmn), which consists of 46 oncogenes and tumor suppressor genes through the Center for Personalized Diagnostics at the University of Pennsylvania. This extensive characterization of common somatic mutations will potentially generate hypothesis that a genotype-therapeutic interaction exists for long term survivors treated with this regimen. In addition, tumor samples obtained at progression will also be subjected to Myseq sequencing to generate hypotheses of mechanisms of resistance to this combination. Archival tissue remaining from genetic analysis will be available for future studies focused on the ER stress response and autophagy using IHC techniques. Similar next generation sequencing platforms at other institutions or from outside vendors may be used. Slides should be requested within the first 6 months of enrollment and shipped to the address provided in 8.3.1 in batches on a periodic basis.

UPCC 21520

8.0 STUDY CALENDAR

Trial Period:	Treatment 0	Cycl	es (28 d	lays	, stı	ıdy a	asse	essr	nents	End of	Post-Trea	itment	
	planned for	D1	of e	ach	сус	le)				•	Treatment			•
Treatment Cycle/Title:	Screening Visit	1	2	3	4	5	6	7	8	Beyond 8 Cycles ¹² 9+	EOT	Safety Follow- up	Follow Up Visits	Survival Follow-Up
Scheduling Window (Days):	-28 to -1		± 3	± 3	At time of Discontinuation	30 days post EOT ⁷	As per standard of care post discon of treatment ⁵	Every 12 weeks⁵						
Informed Consent	Х													
Inclusion/Exclusion Criteria Assessment	х													
Demographics and Medical History	х													
Prior and Concomitant Medication Review	х	х	x	x	x	x	x	x	x	х	х	х		
Drug distribution		Х	Х	Х	Х	Х	Х	X	Х	X				
Post-study anticancer therapy status											Х	Х	Х	х
Survival Status														Х
Adverse Event Assessment	х	х	х	х	х	х	х	х	х	Х	Х	х		
Full Physical Examination	х	х	х	х	х	х	х	х	х	х	Х	х		
Eye Exam ¹⁴	Х		Х					Х		X4				
EKG	Х	Х	Х	Х	Х	Х	Х	Х	Х	X				
Vital Signs and Weight	Х	Х	Х	Х	Х	Х	Х	Х	Х	X	Х	Х		
ECOG Performance Status	х	х	х	х	х	х	х	х	х	х	Х	Х		
Pregnancy Test – Urine or Serum β-HCG ³	х	х												
PT/INR and aPTT	X ¹¹		1	1	1		1							
CBC with Differential ¹⁰	X ¹¹		Х	Х	Х	Х	Х	Х	Х	Х	Х	Х	Х	

UPCC 21520

Trial Period:	Treatment C planned for	reatment Cycles (28 days, study assessments lanned for D1 of each cycle)							essr	nents	End of Treatment	Post-Treatment		
Treatment Cycle/Title:	Screening Visit									Beyond 8 Cycles ¹²	FOT	Safety Follow-	Follow Up Visits	Survival Follow-Up
	VISIC	1	2	3	4	5	6	7	8	9+	201	up		10100-00
Scheduling Window (Days):	-28 to -1		± 3	± 3	± 3	± 3	± 3	± 3	± 3	± 3	At time of Discontinuation	30 days post EOT ⁷	As per standard of care post discon of treatment ⁵	Every 12 weeks⁵
Comprehensive Serum Chemistry Panel ¹⁰	X ¹¹		Х	х	х	Х	х	х	х	x	Х	х	Х	
Transthoracic Echo	х			X ⁴			X ⁴			X4				
Tumor Imaging ⁶	X ⁸		X9		Х 9		X9		X9	X _ð	х		X ¹³	
Tumor biopsies ¹	Х	Х												
Research Blood Collection ²	Х	х	Х	х	х	х	х	х	х	Х	Х			

1. On-study tumor tissue collection is optional and should be performed prior to treatment and then at C1D21±7 days. Preference will be made to biopsy the same site for both biopsies, if safe and feasible.

2. Up to 60mL of blood will be collected for research studies. Please refer to the Study Laboratory Manual for additional details.

3. Female subjects of reproductive potential only. A negative pregnancy test is required within 72 hours of Cycle 1/Day 1.

4. Required q12 weeks (i.e. approximately every 3 cycles). ECHO to be performed between D21-D28 for applicable cycle

- Subjects who discontinue study treatment in the absence of disease progression will have post-treatment follow-up as per standard of care for disease status until one of the following events: (1) disease progression; (2) initiation of non-study cancer treatment; (3) withdrawal of study consent; (4) loss to follow-up; or (5) death. The subject will then enter into survival follow-up. Subjects who discontinue study treatment due to disease progression or initiation of a new anti-cancer therapy will enter survival follow-up directly. Survival follow-up will continue up to 1 year from initiation of study treatment (Cycle 1/Day 1).
- 6. RECIST 1.1 will be used in this study for assessment of tumor response. While either CT or MRI may be utilized, as per RECIST 1.1, CT is the preferred imaging technique in this study. Tumor imaging timing should follow calendar days and should not be adjusted for delays in cycle starts or extension of cycle duration. All visceral areas originally involved by tumor should be re-imaged at each scan interval. The preferred type of imaging is high resolution CT scans of the chest abdomen and pelvis with contrast. In cases of elevated creatinine or anaphylactic reaction to contrast dye, CT scans without contrast or MRI with gadolinium may be substituted for the abdomen and non-contrast CT for the chest.
- 7. The 30 day Safety Follow-up Visit must occur prior to the first dose of any new anti-cancer therapy.
- 8. Baseline tumor imaging to be performed within 30 days prior to Cycle 1/Day 1

UPCC 21520

- 9. Tumor imaging to be performed after every 2 cycles(approximately every 2 months after C1D1 on D21-D28 of applicable cycle).
- 10. CBC with differential including hemoglobin, white blood count, absolute neutrophil count, and platelet count. Serum chemistries including sodium (Na), potassium (K), chloride (Cl), bicarbonate (HCO3), blood urea nitrogen (BUN), creatinine (Cr), albumin, total bilirubin, AST, ALT, and alkaline phosphatase. After Cycle 1, pre-dose laboratory procedures can be conducted up to 72 hours prior to dosing. Results must be reviewed by the investigator or qualified designee and found to be acceptable prior to each dose of trial treatment.
- 11. Screening laboratory tests are to be performed within 10 days prior to Cycle 1/Day 1.
- 12. Treatment will continue indefinitely in the absence of (1), documented disease progression, (2) unacceptable adverse event(s), (3) intercurrent illness that prevents further administration of treatment, (4) investigator's decision to withdraw the subject, (5) subject withdrawal of consent, (6) pregnancy of the subject, (7) noncompliance with trial treatment or procedure requirements, (8) institution of alternative systemic treatment, or (9) other administrative reasons.
- 13. Tumor imaging in post-treatment follow-up will be performed per routine care and at the discretion of the treating investigator.
- 14. See table 3 for required time-points. Suspicion for eye toxicity will prompt an unscheduled research eye exam. To assure the ocular safety of the subjects, at each ocular exam visit the Ophthalmology sub-Investigator will perform a comprehensive eye examination of both eyes. The specified assessments within the ophthalmic examination are reflective of consensus guidelines [American Academy of Ophthalmology Preferred Practice Patterns Committee, 2005] and will be performed according to the Investigator's usual practice in addition to the assessment of visual acuity in the study and will include:

-Ocular alignment and motility, pupillary function, and visual fields by confrontation

-External examination of the eyelids and eyelashes

-Slit-lamp biomicroscopic examination of the anterior segment structures: eyelid margins, conjunctiva, sclera, cornea, anterior chamber, iris, lens, and anterior vitreous

-Intraocular pressure (IOP) measurement

-Following dilation of the pupil, continued slit-lamp biomicroscopic examination of anterior segment structures with clinical grading of lens opacity

-Fundus slit-lamp biomicroscopic examination, including use of accessory diagnostic lenses, to view the vitreous, retina, macula, vasculature, and optic nerve

-if changes on exam or ancillary testing are noted, fundus photography and autofluorescence should be utilized if clinically indicated.

To account for major holidays and unforeseen events such as inclement weather, scheduled visits and testing can occur +/- 1 week, as long as there is documentation as to why they did not occur according to intended schedule. Archival tumor tissue can be obtained at any point during study enrollment and treatment timeline

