5.3 Toxicities and Dose Modifications

Guidelines for specific toxicities are outlined below, but general guidelines for toxicities not listed are provided in Table 5. Of note, if a toxicity is attributable only to one of the investigational drugs, the other investigational agent can be continued if tolerated.

General Dose modification guidelines for binimetinib for toxicities attributable to only binimetinib. These are general guidelines but for specific toxicities dose modification instructions may be different Doses of binimetinib should be adjusted for AEs throughout the study (see Table 1 Recommended Dose Levels). In general, doses should not be reduced or interrupted for Grade 1 AEs unless the AE is a specific ocular AE referred to in the Recommended Dose Modifications Table (see Table 2) but treatment to control symptoms should be provided as appropriate, if applicable.

An individual patient may have their dose of binimetinib reduced to the dose levels in Table 1 below:

Table 1 Recommended Dose Levels

	Binimetinib (mg BID)
Starting Dose	45
Dose Level -1	30
Dose Level -2	15

The lowest recommended dose level of binimetinib is 15 mg BID. When the AE that resulted in a dose reduction improves to and remains stable at the patient's baseline level for a minimum of 14 days, the dose can be re-escalated to the next dose level at the discretion of the Investigator, provided there are no other concomitant toxicities that would prevent drug re-escalation. There is no limit to the number of times the patient can have their dose reduced or re-escalated, however:

- No dose re-escalation of binimetinib is allowed after a dose reduction due to LVEF dysfunction
- No dose re-escalation of binimetinib is allowed after a dose reduction due to retinal toxicity ≥ Grade 2.

Please refer to Dose Modification Table for recommended dose modifications for binimetinib, if applicable, based on the occurrence of treatment-related AEs.

Table 2 Recommended Dose Modifications

In all cases except retina disorders, HCQ may be continued at the discretion of the treating physician

Severity of Adverse Event	Dose Modifications		
Cardiomvopathv			
Asymptomatic, absolute decrease in LVEF of > 10% from baseline that is also	Withhold binimetinib for up to 4 weeks, evaluate LVEF every 2 weeks.		
below the LLN	Resume binimetinib at a reduced dose if the following are present:		
	 LVEF is at or above the LLN and Absolute decrease from baseline is 10% or less and 		

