	Patient is asymptomatic.		
	If LVEF does not recover within 4 weeks permanently discontinue binimetinib.		
Grade 3-4 (Symptomatic congestive heart failure or absolute decrease in LVEF of > 20% from baseline that is also below LLN)	Permanently discontinue binimetinib. Closely monitor LVEF until resolution or up to 16 weeks.		
Venous Thromboembolism			
Uncomplicated DVT or PE	Withhold binimetinib.		
	 If improves to Grade 0-1, resume at a reduced dose. 		
	 If no improvement, permanently discontinue binimetinib. 		
Life threatening PE	Permanently discontinue binimetinib.		
Serous Retinopathy			
Symptomatic serous retinopathy/ Retinal pigment epithelial detachments	 Withhold binimetinib for up to 10 days. If improves and becomes asymptomatic, resume at the same dose. If not improved, resume at a lower dose level or permanently discontinue binimetinib. 		
Retinal Vein Occlusion (RVO) Any Grade	Permanently discontinue binimetinib.		
Uveitis			
Grade 1-3	If Grade 1 or 2 does not respond to specific ocular therapy, or for Grade 3 uveitis, withhold binimetinib for up to 6 weeks.		
	 If improved, resume at same or reduced dose. If not improved, permanently discontinue binimetinib. 		
Grade 4	Permanently discontinue.		

Severity of Adverse Event	Dose Modifications			
Other Eye Disorders (i.e., Non-retinal Eve	ents, non-Uveitis Events			
Grade 1-2	Maintain dose level of binimetinib and increase			
	frequency of ophthalmic monitoring to at least			
	every 14 days until stabilization or resolution.			
Grade 3	Interrupt dosing of binimetinib and refer patient to			
	ophthalmologist within 7 days.			
	• If resolved to Grade ≤ 1 in ≤ 21 days, resume			
	treatment at 1 reduced dose level of			
	binimetinib.			
	 If not resolved to Grade ≤ 1 in ≤ 21 days, 			
	permanently discontinue binimetinib and close			
	follow-up with ophthalmic monitoring until			
	stabilization or resolution.			
Grade 4	Permanently discontinue binimetinib and			
	immediate follow-up with ophthalmic monitoring			
	until stabilization or resolution.			
Interstitial Lung Disease				
Grade 2	Withhold binimetinib for up to 4 weeks.			
	• If improved to Grade 0-1, resume at a reduced			
	dose.			
	• If not resolved within 4 weeks, permanently			
Orada 2 an Orada 4	discontinue.			
Grade 3 of Grade 4	Permanentiy discontinue.			
Hepatotoxicity				
Grade 2 AST or ALT increased	Maintain binimetinib dose.			
	If no improvement within 2 weeks, withhold			

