	binimetinib until improved to Grade 0-1 or to			
	pretreatment/baseline levels and then resume at			
	the same dose.			
Grade 3 or 4 AST or ALT increased	See Other Adverse Reactions			
Rhabdomyolysis or Creatine Phosphokina	ase (CPK) elevations			
Grade 4 asymptomatic CPK elevation or	Withhold binimetinib dose for up to 4 weeks.			
Any Grade CPK elevation with	If improved to Grade 0-1 resume at a reduced			
symptoms or with renal impairment	dose.			
	If not resolved within 4 weeks, permanently			
	discontinue binimetinib.			
Dermatologic				
Grade 2	It no improvement within 2 weeks, withhold until			
	Grade 0-1. Resume at same dose if first			
	occurrence or reduce dose if recurrent.			
Grade 3	Withhold until Grade 0-1. Resume at same dose i			
	TIRST OCCURRENCE OF REDUCE dose if recurrent. If			
	recurrent and already on dose level -2, resume at			
Crada 4	Inal dose.			
Graue 4	Permanentiy discontinue			
Grade 1.2	Maintain doca loval of hinimatinih Dramativ			
Glaue 1-2	institute antiemetic massure			

Severity of Adverse Event Grade 3	Dose Modifications Interrupt dosing of binimetinib until resolved to Grade ≤ 1. Then resume treatment at 1 reduced dose level of binimetinib. Resume treatment with binimetinib at the current dose if, in the judgment of the Investigator, the toxicity is considered to be unrelated to binimetinib, or at 1 reduced dose level.		
	Note: Interrupt dosing of binimetinib for \geq Grade 3 vomiting or Grade 3 nausea only if the vomiting or nausea cannot be controlled with optimal antiemetics (as per local practice).		
Grade 4	Permanently discontinue binimetinib.		
Other Adverse Reactions (including haemorrhage)			
Recurrent Grade 2 or	Withhold for up to 4 weeks.		
First occurrence of any Grade 3	 If improves to Grade 0-1 or to pretreatment/baseline levels, resume at reduced dose. If no improvement, permanently discontinue. 		
First occurrence of any Grade 4	 Permanently discontinue or withhold for up to 4 weeks. If improves to Grade 0-1 or to pretreatment/baseline levels, then resume at a reduced dose. If no improvement, permanently discontinue. 		
Recurrent Grade 3	Consider permanently discontinuing.		
Recurrent Grade 4	Permanently discontinue.		

Investigators should always err on the side of caution in these settings if treatment-related toxicity is a possibility.

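### No scheduled visit explicitly requires CPK, so the binimetinib hold for asymptomatic grade 4 CPK elevation depends on unscheduled testing

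*Combined protocol and SAP*

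**What the plan says.** Section 5.3, Table 2, has a row for rhabdomyolysis or CPK elevation. Its triggers are "Grade 4 asymptomatic CPK elevation or" a CPK elevation of any grade with "symptoms or with renal impairment". The action is to hold binimetinib for up to 4 weeks, resume at a reduced dose if the value falls to grade 0-1, and otherwise stop permanently.

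Section 8.0 schedules a comprehensive serum chemistry panel at screening, from cycle 2 onward, at end of treatment (EOT), at the 30-day safety visit and at later follow-up visits. Footnote 10 gives its contents. The list opens "Serum chemistries including sodium (Na), potassium (K), chloride (Cl" and closes "creatinine (Cr), albumin, total bilirubin, AST, ALT, and alkaline phosphatase". It names eleven analytes, and CPK is not among them. The same footnote adds: "Results must be reviewed by the investigator or qualified designee and found to be acceptable prior to each dose of trial treatment".

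Section 2.3.1 describes most single-agent binimetinib toxicity as grade 1-2 and names creatine kinase elevation as the exception. It gives grade 3-4 rates of 21% in melanoma and 29% in low grade serous carcinoma.

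**The concern.** A dose rule with a symptom-free laboratory trigger works only if someone orders the test. Here the protocol singles out CPK as the toxicity that often reaches grade 3-4 and writes a hold for it, but it does not put the test on any visit. A site that follows the calendar exactly can review every listed result, find each acceptable, and continue binimetinib at 45 mg twice daily in a patient whose CPK is grade 4 and who feels well.

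What is at stake is mainly patient safety. There is also a reporting side. Safety is a co-primary objective, and section 11.5 tabulates observed toxicities and estimates the grade 3 or higher rate. A value that was never measured cannot be tabulated.

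**Working it through.** **Where CPK appears.** It appears in section 2.3.1 as a known toxicity and in Table 2 as a trigger. It does not appear in the calendar rows, the calendar footnotes, the eligibility laboratory table (section 3.1, item 8) or section 10. So no baseline or on-treatment value is explicitly required.

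**Comparable Table 2 rules.**

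| Trigger | Scheduled test behind it |
|---|---|
| "Asymptomatic, absolute decrease in LVEF of > 10% from baseline that is also" below the lower limit of normal | Echocardiogram every 12 weeks; footnote 4: "ECHO to be performed between D21-D28 for applicable cycle" |
| "Grade 2 AST or ALT increased" | Both enzymes named in footnote 10 |
| Retinal and other eye events | Eye examinations, section 5.3.1, Table 3 |
| CPK elevation with symptoms | Adverse event assessment each cycle can prompt a test |
| CPK elevation with renal impairment | Creatinine, named in footnote 10, can prompt a test |
| Asymptomatic grade 4 CPK | None |

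The gap is confined to the last line.

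**How common the toxicity might be.** The inputs are p = 0.21 and 0.29 (section 2.3.1) and n = 10 and 29 (section 11.6). The assumption is that single-agent rates from other tumours carry over to this combination in lung cancer.

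- Expected patients with grade 3-4 elevation, n × p. First 10: 10 × 0.21 = 2.1 and 10 × 0.29 = 2.9. All 29: 29 × 0.21 = 6.09 and 29 × 0.29 = 8.41.
- Chance of at least one, 1 − (1 − p)^n. First 10: 0.905 and 0.967. All 29: above 0.998 at either rate.

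These counts combine grades 3 and 4. The number who would meet the asymptomatic grade 4 trigger is some unknown part of them, so at these rates the counts bound it from above and do not estimate it.

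**Assays needed to close the gap.** Screening 1 + cycles 2 to 8 (7) + EOT 1 + 30-day safety visit 1 = 10 per patient. For 29 patients, 29 × 10 = 290 at most through cycle 8, plus one per later cycle.

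**The case against.** The strongest reply is that Table 2 is a set of recommended modifications, introduced as general guidelines. It says how to react to an event and does not set surveillance. The chemistry panel is called comprehensive and its list is open. Section 6.0 refers to the package inserts. Sections 10.6 and 10.7 call for a site safety monitoring plan and a study-specific data review plan, and none of these can be seen here. The trial is at a single centre, and the text after Table 2 asks investigators to be cautious when treatment-related toxicity is possible. CPK may well be checked routinely.

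Much of this stands. A reader might infer that CPK will not be measured; the documents do not support that, and actual practice cannot be judged from them. What remains is that the written schedule does not require the one test this trigger needs, although it supplies the tests for the comparable rules.

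It may also be asked whether Table 2's catch-all row, which acts on a first grade 3 event, reaches asymptomatic grade 3 CPK. That is arguable. If it does, it too needs a CPK value.

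**Conclusion.** The point holds as a narrow patient-safety gap that should be fixed. No scheduled visit explicitly requires CPK, so the hold for asymptomatic grade 4 elevation depends on testing outside the written calendar. Confidence is high on the omission. The number of patients affected cannot be computed, because no grade 4 rate is given.

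Three stronger readings are tempting and unsupported.

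- **That 6 to 8 patients would miss a hold.** Those counts are for grade 3-4 combined, and some cases would be found through symptoms or creatinine.
- **That the grade 3 or higher rate is understated by a calculable amount, or can only be too low.** Unmeasured elevations may go uncounted. However, the size depends on the share left unmeasured, the overlap with other severe toxicity, and how many values count under section 10.1, which ties laboratory adverse events to active management. None of these is given. A missed hold also prolongs full-dose exposure, which could raise other severe toxicity, so even the net direction is not fixed. The rate is descriptive, and section 11 attaches no decision rule to it.
- **That the objective response rate is certainly unaffected, or is biased.** Missed holds change exposure, and the documents show neither result.

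**What to change.** In footnote 10 of section 8.0, name CPK among the serum chemistries at screening, at each on-treatment chemistry draw (cycle 2 onward), at EOT and at the 30-day safety visit. The safety visit belongs in the list because chemistry is already drawn there and section 10.1 keeps adverse events reportable until 30 days after the last dose.

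The cost is one assay added to each existing draw: about 10 per patient through cycle 8, plus one per later cycle. There may be more dose holds and a higher reported grade 3 or higher rate. The sample size and the two-stage boundaries need no change. Draws remain one 28-day cycle apart, so an elevation arising between visits could still go unseen for up to about four weeks.
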